6.2.4. Additional Visits/Assessment in the VKA-based regimen

For subjects randomized to the VKA-based regimen, INR management may be performed by the Investigator, the subject's primary care physician or other private physician, or at a specialized anticoagulation clinic or patient self-monitoring. Documentation of all INR values must be maintained, including INR tests performed outside of Investigator's site. It is the responsibility of the Investigator or designee to enter all INR results into the eCRF.

The Investigator or designee will measure or collect (by email or fax) the subject's INR value(s) and VKA dose information **at least every month**. Separate documents provided to the sites will inform the Investigator of the recommended frequency of INR monitoring.

For Investigators who are managing INR for subjects assigned to VKA, unscheduled site visits are permissible to achieve and maintain an INR in the target therapeutic range (2.0 - 3.0). The procedures performed at such an unscheduled

visit are identical to those described above for regular on site visits (see section 6.2.1).

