5.4.3. INR Management

Every effort should be made to optimize the VKA dosing and INR monitoring schedule to maintain INR values between 2.0-3.0 inclusive.

INR management is according to the standard of care and may be performed by the Investigator, the subject's primary care physician or other private physician, at

a specialized anticoagulation clinic or patient self-monitoring. Close attention to the INR management plan and frequent monitoring of INR values is strongly recommended to optimize the VKA treatment and maintain the subject's INR values between 2.0-3.0 inclusive. The Investigator will ensure the VKA is used according to the approved label (prescribing information).

Daily INR determinations upon initiation should be obtained until subject's INR is stable in the therapeutic range. It may take 4-14 days to attain the target - - therapeutic range of INR 2'.. 2.0.

Obtain subsequent INR determinations as per recommendations and guidelines provided in the local approved label from the respective VKA manufacturer.

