6.2. Treatment Period

Dates for all visits following the randomization visit are calculated to occur in relation to the randomization visit, with the date of randomization being Day 1.

6.2.1. On-site Visits: 1, 3, 6, and 9 Months (± 7 days) or unscheduled

The following activities and/or assessments are performed at each on site visit:

- Collection of blood samples for the following central laboratory tests:
 - Safety samples for: liver function, serum chemistry, hematology, INR.The samples are processed and sent to the central laboratory (Section 9.6).
- Urine sampling for pregnancy testing for women of childbearing potential (related to women who are pre-menopausal) (local laboratory)
- Dispensation of the assigned study medication and of the medication log to the subject; Medication may be distributed to patients in an unbranded bag for convenience.
- The assigned treatment regimen and the proper daily dosing is explained to the subject including confirmation that the subject understands the proper daily dosing;
- Collection of a 12-lead ECG recording (see section 9.8);

- Local laboratory INR are determined for subjects randomized to VKA;
- Instruction is provided to the subject to bring all study medications to each visit, including edoxaban or VKA, P2Y12 antagonist, and ASA if applicable as well as the filled in medication log;

• The following information is obtained/recorded in the eCRF: - - - - -

- Local laboratory CrCL;
- Kit assignment for edoxaban or VKA, P2Y12 antagonist, and ASA study medications as needed;
- Discontinuation of ASA treatment (1-12 months), according to pre-declaration at randomization
- Next on-site visit is scheduled (i.e. Visit 4, 3 Months; Visit 7, 6 Months; Visit 10, 9 Months).

- The following information is recorded in the eCRF:

- For subjects on VKA, all determined INR values and dose adjustments;
- Any interruptions or dose adjustments of all study anticoagulant and antiplatelet drugs with the date of last dose and the date of the first dose of resumption of drug (Section 5.7). Record this for each of the following separately:
 - Edoxaban or VKA
 - P2Y12 antagonist
 - ASA
- Date of the final dose of ASA in line with pre-declaration at randomization;
- Concomitant medications;
- All endpoints and all AEs experienced by the subject since the last visit.

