9.5. Reporting SAEs/AEs

9.5.1. Documentation

To effectively evaluate the safety profile of the anticoagulant-based regimens, this study will report all (S)AEs occurring after the subject signs the IC and up to 30 days after the last dose of the assigned anticoagulant-based regimen, whether observed by the Investigator or reported by the subject. All AEs will be recorded on the AB/Outcome eCRF page and include:

- Any components of the study endpoint assessments (see Section 7);
- AE that meet seriousness criteria (see Section 9.2.1);
- AE that result in interruption or discontinuation of the assigned anticoagulant-based regimen;
- AE that meet the criteria for AE of special interest (see Section 9.3);
- Any other AE.

All laboratory results and vital signs should be evaluated by the Investigator regarding clinical significance. Isolated abnormal laboratory results or vital sign findings that are not part of a diagnosis should be reported as AEs or SAEs.

Medical conditions (including laboratory values/vital signs that are out of range) that were diagnosed or known to exist prior to IC will be recorded as part of medical history.

All SAEs are to be reported according to the procedures in Section 9.5.2 below.

Always report the diagnosis as the AE or SAE term. When a diagnosis is unavailable, report the primary sign or symptom as the AE or SAE term with

~~additional details included in the narrative until the diagnosis becomes available.~~

If the signs and symptoms are distinct and do not suggest a common diagnosis, report them as individual entries of AE or SAE. For events that are serious due to hospitalization, the reason for hospitalization must be reported as the serious adverse event (diagnosis or symptom requiring hospitalization).

AEs may be directly observed, reported spontaneously by the subject or by questioning the subject at each study visit. Subjects should be questioned in a general way, without asking about the occurrence of any specific symptoms. The Investigator must assess all AEs to determine seriousness, severity, and causality, in accordance with the definitions in Section: 9.2. The Investigator's assessment must be clearly documented in the site's source documentation with the Investigator's signature.

In case of an occurrence of an (S)AE, the Investigator applies the following rules:

- Ensure appropriate medical treatment and decide whether to discontinue or interrupt any of the study medications.

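### Do unscheduled INR visits in the VKA arm bias the bleeding comparison enough to need a change to the plan?

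*Combined protocol and SAP*

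**What the plan says.** Section 6.2.4 states: "For Investigators who are managing INR for subjects assigned to VKA, unscheduled site visits are permissible to achieve and maintain an INR" within the target range. It then says that the procedures at such a "visit are identical to those described above for regular on site visits". The matching list is in Section 6.2.1, whose heading reads "On-site Visits: 1, 3, 6, and 9 Months (± 7 days) or unscheduled". Among other items it requires central laboratory work ("Safety samples for: liver function, serum chemistry, hematology, INR") and recording of "All endpoints and all AEs experienced by the subject since the last visit". Under Section 9.5.1, adverse events may be directly observed, "reported spontaneously by the subject or by questioning the subject at each study visit".

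Two passages bear on how often such visits occur. Section 5.4.3 says "Daily INR determinations upon initiation should be obtained until subject's INR is stable in the therapeutic range". Section 6.2.4 also lets INR be managed by another physician, "or at a specialized anticoagulation clinic or patient self-monitoring".

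Both arms share the schedule in Section 3.1: site visits at months 1, 3, 6, 9 and 12 and telephone calls in the other seven months. Each contact asks about events since the previous one.

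The protocol text names no field for the contact at which a bleed was first detected, and Section 11.3 lists no table of contacts by arm.

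**The concern.** A subject on edoxaban has no INR to control and so no matching reason for an unplanned visit. If VKA subjects are seen and questioned more often, bleeds that would otherwise go unreported may be recorded in that arm only. The blinded Clinical Events Committee cannot correct this, because it adjudicates only what is reported. The named robustness analyses (Sections 11.4.1.1 and 11.4.1.2) vary the analysis set and the analysis period, not detection.

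The direction is clear: extra capture under VKA lowers the edoxaban/VKA hazard ratio. Both primary conclusions, non-inferiority at 1.20 and then superiority, would carry a one-sided error above 2.5%. The planned results for major bleeding and for the single components would show where a difference lies, but not whether treatment or detection caused it.

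**Working it through.** **The plan's own figures (Section 11.9).** HR = ln(0.82)/ln(0.76) = 0.7231. Events for 80% power at two-sided 0.05: 4 × (1.960 + 0.842)² / (ln 0.7231)² = 299. Per arm: 299/(0.24 + 0.18) = 712, as stated. Non-inferiority with 2 × 750 and HR 0.88: D = 750 × (0.24 + 1 − 0.76^0.88) = 341, and Φ(√(341/4) × ln(1.20/0.88) − 1.96) = 81.7%, stated as 82%. No stated figure is in question.

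**Which bleeds could be affected.** Table 17.1 makes a bleed CRNM if it needed medical intervention, led to hospital or a higher level of care, or itself prompted a face-to-face evaluation. A bleed that needs no medical attention is minor and outside the primary endpoint. A bleed merely mentioned at an INR visit did not prompt that visit. A bleed that had already led to care would have to escape the 5 + 7 = 12 scheduled enquiries, any-time reporting (Section 17.9, footnote n) and the collection of bleeding-related outpatient visits (Section 6.2.1). The main remaining route is a bleed first noticed at an INR visit and then treated.

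**When the extra contact falls.** It is likely to be heaviest at VKA initiation, which Section 5.4.3 puts at 4 to 14 days. Section 3.1 places randomization before hospital discharge, so some of those INRs may be taken while both arms are inpatients. The month 1 visit then asks both arms about a short interval.

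**Illustration of size.** The documents supply none of these four inputs; all are assumptions:

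- c = 0.75, CRNM share of first events
- d = 0.10, share of those missed without an extra visit
- f = 0.30, net share of VKA subjects with on-site INR visits
- r, share of their missed bleeds recovered by those visits

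Net under-capture in the edoxaban arm is m = 1 − (1 − cd)/(1 − cd(1 − fr)). The observed HR is h = true HR × (1 − m), with D = 712 × (0.24 + 1 − 0.76^h). The chance of wrongly declaring superiority (true HR 1.00) is Φ(−ln h × √(D/4) − 1.96). The chance of wrongly declaring non-inferiority (true HR 1.20) is Φ(ln(1.2/h) × √(D/4) − 1.96).

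With r = 0.5: m = 1 − 0.925/0.93625 = 1.20%. For superiority, h = 0.988 and D = 340, giving 3.23%. For non-inferiority, h = 1.186 and D = 369, giving 3.26%.

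| d | f | r | m | Superiority | Non-inferiority |
|---|---|---|---|---|---|
| 0.10 | 0.30 | 0.25 | 0.60% | 2.85% | 2.86% |
| 0.10 | 0.30 | 0.5 | 1.20% | 3.23% | 3.26% |
| 0.10 | 0.30 | 1 | 2.37% | 4.10% | 4.18% |
| 0.10 | 0.10 | 0.5 | 0.40% | 2.73% | 2.74% |
| 0.10 | 0.60 | 0.5 | 2.37% | 4.10% | 4.18% |
| 0.05 | 0.30 | 0.5 | 0.58% | 2.83% | 2.85% |
| 0.20 | 0.30 | 0.5 | 2.58% | 4.27% | 4.36% |

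Visits early in titration cannot recover late bleeds, so r well below 1 is the more realistic reading. The error reaches 5% at m = 3.38% (superiority) or 3.24% (non-inferiority). In edoxaban-arm events, that is 712 × (0.76^0.9662 − 0.76) ≈ 5 of 171, or 5 to 6 of 200. With d = 0.10 this needs f × r of about 0.43 or 0.41, against 0.30 × 0.5 = 0.15 in the worked case. With no on-site INR visits the effect is nil.

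**Earlier dates only.** If the visits add no events but bring VKA event dates forward by a mean of 7 to 30 days, a simulation at true HR 1.00 gives an HR of about 0.99 to 0.975 (Monte Carlo error 0.005 to 0.006). Section 11.4 analyses time to first occurrence, so dating by onset removes this part.

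**The case for a change.** The strongest case for acting is that the asymmetry is written into the protocol and always points the same way, and that very few events are enough to matter. Larger assumptions give larger errors. With 750 per arm, a 5% rise in the detected VKA hazard (about 8 more VKA subjects with an event) gives 6.8% for superiority and 7.0% for non-inferiority. Extra haematology might also reveal a haemoglobin fall that moves an overt bleed into the major class, so the major-bleeding result is not fully protected. The detecting contact is best recorded when the event is entered, and a field and a table cost little.

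The direction and the sensitivity to small numbers stand. The size does not. A 5% rise means m = 1 − 1/1.05 = 4.76%, which with c = 0.75 and d = 0.10 needs f × r of about 0.62. That requires most VKA subjects to attend and most missed bleeds to be recovered.

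The possible remedies are weaker than they look:

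- **Limiting INR visits to INR and VKA dose.** This thins safety assessment in the arm that also receives ASA. It replaces a required enquiry with volunteered or investigator-noticed events, which is its own source of bias in an open-label trial. It would also conflict with the compliance check at each visit (Section 5.8 and Section 17.9, footnote m).
- **A sensitivity analysis without bleeds that qualify only by face-to-face evaluation.** A bleed found at an INR visit and then treated qualifies by medical intervention and stays in, while bleeds that truly prompted an evaluation are removed.
- **A detection field and a contact table.** These change no planned result. All INR results, unscheduled laboratory measurements and event pages already go into the study data, so contacts could probably be counted without an amendment. The separate SAP, CEC charter and Study Operations Manual are not part of the text reviewed and may already cover this.

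**Conclusion.** The reading of Section 6.2.4 is correct, and some excess capture of mild bleeds under VKA is possible. It is not a defect that calls for a change. The visits are optional, INR may be managed off site, and the common monthly enquiry together with the CRNM definition leaves a narrow route. Under the assumed inputs with r of 0.25 to 0.5, the one-sided error is about 2.9% to 3.3% instead of 2.5%. It would be nil if no such visits take place and above 5% only under much heavier attendance or recovery, or many more missed bleeds. All of this rests on assumed values of c, d, f and r.

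Keeping the full enquiry at these visits is a fair trade-off between safety data and strict symmetry. The report can present CRNM alone beside ISTH major bleeding, both already planned under Section 7.2. The sponsor may, at its option, also count unscheduled contacts by arm or record where each bleed was first detected. No rule or figure in the plan is shown to be wrong.

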6.2.5. Missed Follow up Visits

Every effort should be made to ensure subjects return for their on-site visits. If the subject is unable to return for an on-site visit, the Investigator, or designee, must document in the patient record the reason the subject was unable to complete the visit. The Investigator should also make every effort to contact the subject, within the visit window, to collect the subject's vital status as well as information related to potential adverse events, safety data, and hospitalizations.

6.3. Post-treatment Period

6.3.1. On-site Visit: 1 month post-EOT (\pm 7 days)

All subjects on edoxaban or VKA at 12 months (EOT visit), have a visit planned 30 days thereafter.

Subjects who prematurely discontinued their assigned OAC **Will** not require an additional follow-up visit or telephone contact after the End of Study Visit apart from patients withdrawn due to AEs (see section 4.3.1 and 4.3.2).

The following wUI be performed at the post-EOT visit:

- Record targeted concomitant medications;
- Collection of a 12-lead ECG recording (see section 9.8);
- Vital signs;
- Record all endpoints and all AEs experienced by the subject since the last visit.
 - Endpoint and other event reporting (including hospitalization) will be done throughout the study as soon as site personnel learn of the endpoint/event; For subjects who experience a stroke event after randomization, the Investigator will evaluate the residual disability by modified Rankin score at the time of discharge from the hospital (see Section 17.7).
 - Record any treatments (drug and non-drug) given for endpoint events and AEs since the last visit.
 - Record any hospitalizations, PCI procedures, and CABG procedures since the last visit.

6.4. Protocol Deviations

The Investigator conducts the study in compliance with the protocol agreed to by sponsor and, if required, by the regulatory authority(ies) and by the EC.

Actions taken to eliminate immediate subject hazard(s) that deviate from any protocol procedures are marked/ flagged as a deviation. The sponsor and site monitor must be notified of all intended or unintended deviations to the protocol.

(e.g., inclusion/exclusion criteria, dosing) on an expedited basis. The Investigator, or person designated by the Investigator, should document and explain any deviation from the approved protocol and notify the EC of any protocol deviations in accordance with local procedures.

Even if a subject was ineligible or inadvertently received the incorrect drug or dosage, discontinued or interrupted the assigned treatment regimen, or refused to further undergo on-site visits, clinical follow-up data should still be collected up to 12 months after randomization (EOT).

6.5. Modification of IC after Randomization

Subjects are scheduled to have regular study contacts every month until the 12-month EOT visit is completed.

In accordance with the Declaration of Helsinki and other applicable regulations, a subject has the right to withdraw consent from study participation at any time and for any reason without prejudice to his or her future medical care by the physician or at the institution.

This protocol makes a distinction between request to discontinue (1) any or all study medication, (2) on site visits, (3) telephone contacts, (4) collection of clinical follow-up data, (5) collection of vital status and (6) full withdrawal of IC.

All subjects are followed for 12 months irrespective of changes in the antithrombotic regimen. Henceforth, during interruption or following discontinuation of study medication, subjects continue to have regular study visits or telephone assessments until the 12-month EOT visit is completed.

If the subject cannot return for an in-person visit, a telephone visit is scheduled unless subject requests not to be contacted by telephone. Collection of available clinical data or vital status, either at the interventional center, at the referring hospital, with the general practitioner, or the municipal registries continues unless explicitly disallowed by subject.

Collected data up to the date of full withdrawal of IC are used in the final analysis.

Records in the eCRF document modifications to the IC as detailed above (incl. level and date of modification or withdrawal).

6.5.1. Subjects Lost to Follow-Up

All subjects should be encouraged to return for protocol-required on-site visits or telephone assessments for evaluation during the clinical follow-up. If a subject is unable to return for a clinic visit, subject should be contacted by telephone to obtain subject required information. All attempts should be documented in the

source documents. If the subject does not respond to telephone calls, then the Investigator must send a certified letter to the subject. Only after failing to contact the subject at the final follow-up visit will the subject be considered lost to follow-up after last contact except for mortality if available via municipality registries. It must be a high priority to obtain at least survival data on all subjects lost to follow-up. When a subject is lost to follow-up a study End-of-Study Form is completed.

6.6. End of Trial Definition

All subjects on OAC study medication (edoxaban or VKA) at 12 months, have a contact planned 1 month after the EOT visit, to collect data on targeted concomitant medications, SAEs, and other events of interest. The final contact is either the scheduled EOT visit at 12 months or the post-treatment follow-up visit scheduled at 13 months. The study completion is reached as soon as the final contact of the last subject is performed in all centers and in all participating countries.

7. OUTCOME ASSESSMENTS

7.1. Primary Endpoint

The primary endpoint is the composite of major or clinically relevant non-major bleeding (MCRB) defined according to the ISTH-defined bleeding definitions, analyzed as time to first occurrence of any component.

7.2. Secondary Exploratory Endpoints

The secondary endpoints are defined as:

- Main efficacy endpoint (MEE), defined as the composite of cardiovascular (CV) death, stroke, systemic embolic events (SEE), myocardial infarction (MI) and definite stent thrombosis.
- Net clinical benefit (NCB), defined as the composite of CV death, stroke, SEE, MI, definite stent thrombosis and ISTH-defined major bleeding.
- Main thromboembolic event, defined as composite of cardiac or thromboembolic death (thromboembolic death considered to be thromboembolic in origin (including thromboembolic stroke, pulmonary embolism, any other systemic embolism), ischemic stroke, SEE, MI and definite stent thrombosis.

ISTH-defined major bleeding

- Any bleeding defined as the composite of major, clinically relevant non-major and minor bleeding (ISTH definition)

Symptomatic intracranial hemorrhage (ICH)

- Composite of stroke and SEE

Composite of all-cause death, stroke, SEE, MI and definite stent thrombosis

Composite of CV death, MI and definite stent thrombosis

- The single components of the composite primary and secondary endpoints mentioned above are explored, as well as specific subcategories (e.g., hemorrhagic, ischemic and undetermined stroke)

Safety parameters such as (serious) adverse events, laboratory parameters, ECG and vital signs.

All secondary endpoints are analyzed as time to first occurrence of any of its components.

Bleeding events are also classified according to Bleeding Academic Research Consortium (BARC) and Thrombolysis in Myocardial Infarction (TIMI) classifications for descriptive purposes only. All suspected bleeding events are adjudicated by the CEC in a blinded manner.

All events are also sub-categorized into fatal and non-fatal.

For all endpoints blindly adjudicated by the CEC, the CEC's interpretation prevails and is used in the statistical analyses.

7.3. Endpoint definitions

All suspected endpoint events are adjudicated by an independent CEC (see section 17.1.2) without knowledge of the actual assigned treatment. The adjudication criteria are mentioned below. Further details on these definitions and how they will be assessed are provided in the CEC Charter. The requirements for collecting and submitting the source documents for appropriate adjudication of the reported primary and secondary endpoint events will be provided to the sites/Investigators separately in the Study Operations Manual.

For all endpoints blindly adjudicated by the CEC, the CEC's interpretation prevails and is used in the statistical analyses.

